10.3.1. Key Secondary Endpoints

The key secondary efficacy endpoints include ORR and EFS assessed by an Independent Response Assessment Committee (IRAC) and by local investigators based on modified International Working Group (IWG) AML response criteria. Details of the procedure used to proceed IRAC assessed IWG and CR/CRh responses, and the IRAC assessed HI response can be found in the separate IRAC Charter.

10.3.1.1. Overall Response Rate

Overall response rate (ORR) is defined as the rate of Best Response in CR + CRi + CRp + partial remission (PR) + morphologic leukemia-free state (MLFS) according to modified IWG AML response criteria.

The ORR will be summarized by treatment group and be compared between arms by the Cochran-Mantel-Haenszel (CMH) test with stratification factors:

- Prior intensive therapy for AML: yes versus no
- Primary refractory: yes versus no
- Prior allogeneic HSCT for AML: yes versus no

If a stratification factor covariate has less than 40 subjects in one of its levels across treatment groups, then this factor will not be used in stratified analysis. This analysis based on IRAC assessment in the ITT population will be used as the main analysis of ORR.

As sensitivity analyses, a CMH test with the above strata will be performed in the mITT population. In addition, a Fisher's exact test without stratification factors will be performed in both ITT and mITT population. An Odds Ratio and its 95% C.I. of responders versus non-responders between treatment arms will also be calculated. This analysis will be repeated for the local assessment of response as a supportive analysis of ORR.

Additionally, overall response rate will be repeated for a Dose group analysis of AG-221 subjects who had at least one dose > 100mg during the study versus those who received only dose ≤100mg.

10.3.1.2. Event-Free Survival

Event-free survival (EFS) is defined as the period from the date of randomization to the date of documented morphologic relapse (hereafter referred as relapse) after CR/CRi/CRp, PD according to modified IWG AML response criteria or death from any cause, whichever occurs first. Subjects who are alive without any of these events will be censored at the date of their last valid response assessment. Subjects who do not have post-randomization response assessment will be censored at date of randomization.

If a subject begins a new anti-cancer therapy prior to documented disease progression (or death), the subject will be censored at the date of last assessment before starting the new anti-cancer therapy. Subjects with two or more consecutive missing response assessments prior to documented progression (or death) will be censored at the last date of response assessment before the missing assessments.

Analysis of EFS will be similar to the analysis of OS. The stratified log-rank test based on the ITT population will be considered the primary analysis for EFS, with unstratified analyses and the analyses based on mITT populations considered supportive analyses. The analysis based on local assessment of response will be conducted as a supportive analysis of EFS.

Additionally, EFS will be repeated for a Dose group analysis of AG-221 subjects who had at least one dose > 100mg during the study versus those who received only dose ≤100mg.

Table 4: Censoring Rules for EFS

Value of Event-free Survival Date (ADT)	Censored (Y,N)	Derivation
ADT = min(death date, relapse date, progression date)	N	If a subject died, relapsed, or had disease progression by independent review, and the subject has less than two consecutive missing response assessments prior to a visit documented death, relapse, or progression which is before any subsequent anti-cancer therapies
ADT = the last event-free assessment date before missing assessments/ randomization date	Y	If a subject died, relapsed, or had disease progression by independent review, and the subject has two or more consecutive missing response assessments prior to a visit documented death, relapse, or progression
ADT = the last assessment date/randomization date	Y	If a subject did not die, or did not have relapse or progression, and did not receive any subsequent anti-cancer therapies. If there was no post-randomization response assessment, then ADT = the randomization date.
ADT = the last assessment date on or prior to start of subsequent anti-cancer therapies/randomization date	Y	If a subject did not die, or did not have relapse or progression on or prior to start of subsequent anti-cancer therapies. If there was no post-randomization response assessment on or prior to subsequent therapies, then ADT = the randomization date.
ADT = the last assessment date on or prior to start of subsequent anti-cancer therapies/randomization date	Y	If a subject died, relapsed, or had disease progression by independent review after receiving subsequent anti-cancer therapies. If there was no post-randomization response assessment on or prior to subsequent therapies, then ADT = the randomization date.
ADT = analysis date; N = no; Y = yes.		
Note: Event-free response refers to a response that was neither morphologic relapse, progressive disease (PD) nor death.		

Sensitivity analyses for EFS will be done with the following censoring rules:

- Subjects with two or more consecutive missing response assessments prior to an event date (death, relapse or disease progression) will not be censored at the last date of last response assessment before the missing assessment;
- Subjects with subsequent anti-cancer therapies or with two or more consecutive missing assessments prior to an event date will not be censored;
- Subjects with subsequent transplantation after treatment will not be censored;
- Subjects with off-protocol AG221 prior to an event will not be censored;
- Subjects with any anti-cancer therapies (including AML therapy, any therapy for diseases other than AML excluding hydroxyurea) prior to an event date will not be censored.

Other sensitivity rules may be added when data is applicable.

10.3.2. Other Secondary Endpoints

The other secondary endpoints include duration of response, time to response, rates of overall remission, CR, complete remission rate and HI rates assessed by an IRAC and by local investigators according to modified IWG AML response criteria and IWG myelodysplastic syndromes (MDS) HI criteria, treatment mortality at 30- and 60-day, one-year survival, rate of HSCT and time to treatment failure. CR/CRh rate, duration of CR/CRh, and time to CR/CRh assessed by IRAC only and using a sponsor derived assessment will also be presented.

10.3.2.1. Duration of Response

Duration of response is defined as time from first documented CR/CRi/CRp/PR/MLFS to documented morphologic relapse, PD, or death due to any cause, whichever occurs first. Subjects without morphologic relapse, PD, or death due to any cause will be censored at the date of the last valid response assessment.

The duration of response will be analyzed using the KM method. The 25th percentile, median and 75th percentile time (including two-sided 95% CI) will be summarized for each treatment arm. Only subjects with documented CR/CRi/CRp/PR/MLFS response as determined by the IRAC will be included in the analysis. Investigator assessed results will be summarized as a supportive analysis.

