#### 9.6.2.2. Additional Secondary Efficacy Analyses

The other secondary endpoints include duration of response, time to response, rates of overall remission, CR and HI assessed by an IRAC according to modified IWG AML response criteria ([Appendix F](#)) and IWG MDS HI criteria ([Appendix H](#)), treatment mortality at 30 and 60 days, one-year survival, rate of HSCT and time to treatment failure. The definitions of these additional secondary efficacy endpoints are listed below and in Section 2.

**Duration of response** is defined as time from first documented MLFS/CR/CRi/CRp/ PR to documented morphologic relapse after CR/CRi/CRp/ PD or death due to any cause, whichever occurs first. Subjects without morphologic relapse, PD or death due to any cause will be censored at the date of the last response assessment.

**Time to response** is defined as time from randomization to first documented MLFS/CR/CRi/CRp/ /PR. Subjects without a MLFS/CR/CRi/CRp/ PR will be censored at the date of the last response assessment.

**Treatment mortality at 30 and 60 days** is defined as rate of death from any cause within 30 or 60 days of initiation of study treatment.

**One-year survival** is defined as the probability of survival at 1 year from randomization.

**Overall remission rate** is defined as rate of CR + CRi + CRp according to modified IWG AML response criteria ([Appendix F](#)).

**Complete remission rate** is defined as rate of CR according to modified IWG AML response criteria ([Appendix F](#)).

**Hematologic improvement rate** is defined as rate of neutrophil response (hematologic improvement neutrophil response [HI-N]) + platelet response (hematologic improvement platelet response [HI-P]) + erythroid response (hematologic improvement erythroid response [HI-E]) according to IWG MDS HI criteria ([Appendix H](#)).

**Rate of HSCT** is defined as rate of bridge-to-HSCT through study treatment.

**Time to treatment failure** is defined as time from randomization to discontinuation of study treatment due to any cause.

The rate of CR/CR with partial hematologic recovery (CRh; [Appendix F](#)) and duration of CR/CRh will be analyzed using the statistical methods mentioned above or other statistical methods as appropriate. Note: CRh is not available for the investigator's assessment and will be assessed by the Sponsor only and based on laboratory dataset.

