15.5. International Working Group Acute Myeloid Leukemia Response Criteria

Hematologic Response According to modified IWG Criteria for AML	
Category	Definition
Morphologic Complete Remission (CR)	Defined as less than 5% blasts in a BM aspirate sample with marrow spicules and with a count of at least 200 nucleated cells. There should be no blasts with Auer rods and absence of extramedullary disease. Plus, all the following conditions should be met: 
 ANC $\geq 1 \times 10^9/L$ (1,000/μL) Platelet count $\geq 100 \times 10^9/L$ (100,000/μL) Independent of red cell transfusions for ≥ 1 week immediately before each response assessment
Morphologic Complete Remission with Incomplete Neutrophil Recovery (CRi)^a	Defined as all criteria of morphologic CR except the following: 
 ANC $< 1 \times 10^9/L$ (1,000/μL)
Morphologic Complete Remission with Incomplete Platelet Recovery (CRp)^a	Defined as all criteria of morphologic CR except the following: 
 Platelet count $< 100 \times 10^9/L$ (100,000/μL)
Morphologic Complete Remission with Partial Hematologic Recovery (CRh)^a	Defined as all criteria of morphologic CR except the following: 
 ANC $> 0.5 \times 10^9/L$ (500/μL), and Platelet count $> 50 \times 10^9/L$ (50,000/μL)
Morphologic Leukemia-free State (MLFS)	Defined as less than 5% blasts in a BM aspirate sample with marrow spicules and with a count of at least 200 nucleated cells. There should be no blasts with Auer rods and absence of extramedullary disease
Partial Remission (PR)	Defined as all hematologic criteria of morphologic CR with a $> 50\%$ decrease in the percentage of BM blasts to 5% to 25% (a blast count value of $< 5\%$ may also be considered a partial remission if Auer rods are present) ^b
Cytogenetic Complete Remission (CRc)	Defined as CR/CRi/CRp with a reversion to a normal karyotype in cases with an abnormal karyotype at baseline, based on evaluating ≥ 20 metaphase cells from BM
Morphologic Relapse after CR/CRi/CRp^a	Defined as one of the following conditions: 
 Reappearance of $\geq 5\%$ blasts in the BM not attributable to any other cause (e.g., BM regeneration after consolidation therapy); or Development of extramedullary disease
Not evaluable (NE)^a	Defined as without a post-treatment response assessment

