Stable Disease (SD)^a	Defined as failure to meet any of the above criteria and not meeting the criteria of progressive disease (see below)

Progressive Disease (PD) ^a	
Defined as one of the following conditions:
 
 • For subjects with 5 to 70% BM blasts at baseline: a > 50% increase of BM blast count percentage from baseline to $\geq 20\%$; or • For subjects with > 70% BM blasts at baseline: a doubling of absolute blast count in peripheral blood from baseline to $\geq 10 \times 10^9/L$ (10,000/μL); or • Development of new extramedullary disease since last response assessment 
Progressive disease is to be confirmed by 2 consecutive response assessments separated by at least 1 month. The date of progressive disease is defined as the first date that one of three conditions listed above was met.

--	---

AML = Acute Myeloid Leukemia; ANC= Absolute Neutrophil Count; BM= Bone Marrow; IWG= International Working Group.

^a Modification to IWG response criteria.

^b If the pre-treatment bone marrow blast percentage was 50% to 100%, the percentage of blasts must decrease to a value between 5% and 25%; if the pre-treatment blast percentage was 20% to less than 49%, they must decrease by at least half to a value of more than 5%.

Notes: Deletions to the IWG response criteria are not shown.

Source: [protocol Appendix F](#).

15.6. Hematologic Improvement According to the International Working Group for Myelodysplastic Syndromes

Hematologic Improvement According to IWG Criteria	
Hematologic improvement ^a	Response criteria (responses must last at least 8 week) ^b
Erythroid Response (HI-E) (pre-treatment, < 11 g/dL)	
 Hemoglobin increase by ≥ 1.5 g/dL Relevant Reduction in units of RBC transfusions by an absolute number of at least 4 RBC transfusions/8 week compared with the pretreatment transfusion number in the previous 8 weeks 
Note: Only RBC transfusions given for a hemoglobin of ≤ 9.0 g/dL on treatment will count in the RBC transfusion response evaluation ^b

Platelet Response (HI-P) (pre-treatment, < $100 \times 10^9/L$)	
 Absolute increase of $\geq 30 \times 10^9/L$ for subjects starting with $> 20 \times 10^9/L$ platelets Increase from $\leq 20 \times 10^9/L$ to $> 20 \times 10^9/L$ and by at least 100% ^b

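### Duration of response can run through leukemia regrowth when the best response is MLFS, PR or CRh alone, because relapse exists only after CR/CRi/CRp and PD is measured from baseline

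*SAP*

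**What the plan says.** **Start and end of the clock.** SAP 10.3.2.1: "Duration of response is defined as time from first documented CR/CRi/CRp/PR/MLFS to documented morphologic relapse, PD, or death due to any cause". Subjects with none of these events are censored at their last valid response assessment. SAP 10.3.2.12 ends duration of CR/CRh at the same three events.

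**Relapse.** The only relapse category in SAP 15.5, as in protocol Appendix F, is titled "Morphologic Relapse after CR/CRi/CRp". It is met when marrow blasts return to 5% or more, or when extramedullary disease develops. SAP 10.3.2.1 does not repeat the limit to CR/CRi/CRp, but protocol 9.6.2.2 does so for duration of response: "documented morphologic relapse after CR/CRi/CRp/ PD or death due to any cause, whichever occurs first" (I read the stray slash before PD as a separator).

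**PD.** SAP 15.5 gives three routes:
- "For subjects with 5 to 70% BM blasts at baseline: a > 50% increase of BM blast count percentage from baseline to" at least 20%;
- "For subjects with > 70% BM blasts at baseline: a doubling of absolute blast count in peripheral blood from baseline to" at least 10 x 10^9/L;
- "Development of new extramedullary disease since last response assessment".

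PD must be confirmed at least a month later and is dated to the first time a condition was met. Anything that meets neither a response category nor PD is stable disease.

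**EFS.** SAP 10.3.1.2 uses "documented morphologic relapse (hereafter referred as relapse) after CR/CRi/CRp, PD according to modified IWG AML response criteria or death from any cause". The note to its censoring table treats every assessment other than relapse, PD or death as event-free.

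**The concern.** The responses that open the clock and the events that close it do not match. MLFS uses the same marrow criterion as CR (blasts below 5%), and so does CRh. Yet the 5% trigger that ends a CR is not defined for MLFS, or for a CRh that is neither CRi nor CRp. PR has no loss-of-response event at all. For these subjects the only marrow-based event is PD, and PD looks back to baseline, not to the best level reached.

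At stake is whether the reported duration measures time in response. A subject who has lost MLFS but not reached PD is classed as stable disease, and the clock keeps running. It then runs to PD, to death or to censoring at a last assessment that may itself show the regrowth. SAP 10.3.2.1 states no rule for new anti-cancer therapy, so a death after a change of treatment could, as written, be the date on which the response ends.

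**Working it through.** The plan gives no figure for duration of response, so there is none to reproduce. The check traces the definitions and computes the PD threshold.

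**Step 1. Marrow level needed for PD.** Input: the first PD route in SAP 15.5, reading the increase as relative. For a baseline of B% between 5 and 70, PD needs blasts above 1.5 x B and at least 20%, so the threshold is max(1.5 x B, 20).

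| Baseline marrow blasts | 1.5 x baseline | PD threshold after MLFS or PR | Relapse threshold after CR/CRi/CRp |
|---|---|---|---|
| 5% | 7.5% | 20% | 5% |
| 10% | 15% | 20% | 5% |
| 20% | 30% | above 30% | 5% |
| 40% | 60% | above 60% | 5% |
| 60% | 90% | above 90% | 5% |
| 70% | 105% | cannot be reached | 5% |
| above 70% | not used | no marrow route; peripheral blasts only | 5% |

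The 20% floor governs below 20 / 1.5 = 13.3%. The marrow route cannot be met above 100 / 1.5 = 66.7%. Between those two values the trigger is a rise of more than half over baseline.

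**Step 2. Worked case, MLFS.** Baseline 40%, MLFS at 3%, then 55%. Since 55 is below 60, this is not PD. The subject was never in CR, CRi or CRp, so it is not relapse. The category is stable disease and there is no duration event, although blasts exceed the pre-treatment level. After CR, the same course is a relapse once blasts reach 5%.

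**Step 3. Worked case, PR.** Baseline 40%, PR at 15%, then 55%. The result is again stable disease. The 5% trigger cannot be borrowed here, because PR already allows 5% to 25% blasts.

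**Step 4. Worked case, CRh.** Read literally, CRi waives only the neutrophil criterion and CRp only the platelet criterion, while CRh relaxes both. Neutrophils of 0.7 and platelets of 70 (x 10^9/L) meet CRh but neither CRi nor CRp. The relapse that should end this subject's duration of CR/CRh is not defined for that subject.

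**Step 5. Who is affected.** Only subjects who never reach CR, CRi or CRp. Someone who moves from MLFS or PR to one of these and then relapses has an event.

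**The case against.** **The definition may be broader than it looks.** SAP 10.3.2.1 and 10.3.2.12 say relapse without the limit, and reappearance of 5% blasts can be applied to anyone who fell below 5%. SAP 10.3.1 also refers response procedures to an IRAC charter, which is not among the documents. This stands in part: it shows that two derivations are possible. But protocol 9.6.2.2 takes the narrow one expressly, and even the broad one leaves PR uncovered.

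**A reader might infer that nothing counts until blasts exceed baseline by half.** That goes too far. Death and new extramedullary disease count at any blast level, the 20% floor applies at low baselines, and baselines above 70% use peripheral blasts.

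**A reader might infer a delay of at least one marrow interval.** The documents do not support a minimum. Blasts can pass both 5% and the PD threshold between two marrows, and PD is dated to the first qualifying assessment. Marrows are also taken before Cycles 2 and 3 and when clinically indicated, so intervals are not uniformly 8 or 12 weeks. Events can be delayed; they need not be.

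**A reader might infer that EFS is mis-defined and should be changed.** EFS does not depend on response. A never-responder going from 40% to 55% is equally stable disease and equally event-free. The baseline-referenced PD rule is prespecified, and both documents mark the relapse and PD rows as modifications of the IWG criteria. EFS is a key secondary endpoint in the testing sequence, and the trial is open-label with its interim completed in March 2019, so redefining EFS now carries a real cost. What remains is that the EFS sensitivity analyses listed in SAP 10.3.1.2 change only censoring; none adds loss of MLFS as an event.

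**The consequence is limited.** Duration of response is summarised by Kaplan-Meier without a between-arm test and lies outside the hierarchy in SAP 10.1. This stands, and it bounds the point.

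**Conclusion.** The point holds for duration of response and duration of CR/CRh. Followed as written in the protocol, the rules give a wrong duration for a subject whose best response is MLFS or CRh alone and whose marrow regrows short of PD. They leave loss of PR without any event short of PD or death.

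Per subject, the gap runs from 5% up to the PD threshold: 20% at a 5% baseline, above 60% at a 40% baseline, and no reachable marrow threshold above 66.7%. The direction is towards overstated duration. The total cannot be computed, because neither document gives the MLFS/PR share of responders or a regrowth rate. For the same reason a difference in bias between arms is possible but not shown. OS and its sizing at 250 deaths are not touched.

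This rests on three assumptions: the PD increase is relative; the CRi and CRp definitions are read literally; and the IRAC charter does not already contain a loss-of-response rule.

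**What to change.** 1. In SAP 10.3.2.1 and 10.3.2.12, count a return to at least 5% marrow blasts, or extramedullary disease, after MLFS or CRh as relapse, on the same terms as after CR/CRi/CRp. Apply it to both the IRAC and the sponsor-derived CR/CRh.
2. Align this with protocol 9.6.2.2 and record it in SAP Section 13 before the final database lock. Align Table 2 in SAP 4.2.2 too: its entry for duration of CR/CRh omits PD, which 10.3.2.12 includes.
3. Show duration of response for CR/CRi/CRp separately.
4. Add a duration-of-response sensitivity analysis that counts loss of PR, and state the threshold in advance. One candidate is a rise above the 25% ceiling in the PR row. It adds events only at baselines above 25 / 1.5 = 16.7%, since below that PD is already met at or under 25%.
5. Leave the primary EFS definition unchanged. Add one EFS sensitivity analysis that counts loss of MLFS (at least 5% marrow blasts) as an event.

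The cost is a little more derivation work, from marrow data that are already reviewed centrally, and a reported duration of response that may be slightly shorter.

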### 6.3. Follow-up Phase

All subjects discontinued from study treatment for any reason other than withdrawal of consent for follow-up will continue to have the following assessments in the Follow-up Phase:

[figure not shown]
- AEs, [REDACTED] concomitant medications, concomitant procedures and transfusions for 28 days after the last study treatment or the EOT visit, whichever is longer.

Thereafter, SAEs made known to the investigator at any time that are suspected of being related to study treatment, as described in Section 10.1.

- Transfusions [REDACTED] will continue to be collected until the initiation of the first subsequent AML therapy after discontinuation from study treatment, death, lost to follow-up, withdrawal of consent for further data collection, or the End of Trial, whichever occurs first.
- Bone marrow aspirate and/or biopsy, peripheral blood smear and, if applicable, cytogenetics, available for both local and central review for assessing response or

disease status, every 12 weeks ( $\pm$  28 days) or more frequent if clinically indicated until PD, the initiation of the first subsequent AML therapy after discontinuation of study treatment, death, lost to follow-up, withdrawal of consent for further data collection, or the End of Trial, whichever occurs first.

- Response/disease status and HI will be assessed whenever bone marrow samples are collected for assessing response or disease status (see above)

- Survival follow-up every 4 weeks ( $\pm$  7 days) until death, lost to follow-up, withdrawal of consent for further data collection, or the End of Trial, whichever occurs first. Subsequent AML therapies should be collected at the same schedule as survival follow-up.
- Investigator-assessed response/ disease status to subsequent AML therapies will be collected. Specifically, the best response to a subsequent AML therapy and the first date achieving the best response, and progressive disease/relapse date during or after a respective subsequent AML therapy should be reported.
- Survival follow-up, subsequent AML therapies, and response/ disease status to subsequent AML therapies may be conducted by record review (including public records) and/or telephone contact with the subject, family, or the subject's treating physician.

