8.4.3. Prior/Follow-up Anti-Cancer Therapies

This section includes both AML therapies and non- AML therapies. AML therapies include surgery, radiation, systemic or any other therapy for the subject's AML disease, particularly intensive AML chemotherapies as induction/re-induction/salvage chemotherapies, consolidation or maintenance therapies, HSCT, low-intensity AML therapies such as azacitidine, decitabine or LDAC, or other medications considered supportive care for AML, regardless of discontinuation

date of treatment. Non-AML therapies may consist of the same therapies like AML therapies but for other hematologic or non-hematologic malignancies.

All tables described in this section will be produced on both ITT and safety population.

Prior and follow-up therapies will be summarized separately in tables.

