10.3.2.12. Duration of CR/CRh

Duration of CR/CRh is defined as time from first documented CR or CRh to documented morphologic relapse, PD, or death due to any cause, whichever occurs first. Subjects without morphologic relapse, PD, or death due to any cause will be censored at the date of the last response assessment.

The duration of CR/CRh will be analyzed using the KM method. The 25th percentile, median and 75th percentile time (including two-sided 95% CI) will be summarized for each treatment arm. Only subjects with CR/CRh response will be included and will be summarized for both IRAC and sponsor assessed responses.

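### Duration of response and duration of CR/CRh have no new-therapy rule, so once a responder starts subsequent AML therapy the censoring depends on the later outcome

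*SAP*

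**What the plan says.** - **Duration of response, SAP 10.3.2.1.** The clock runs from first response to relapse, PD or death from any cause. For everyone else: "Subjects without morphologic relapse, PD, or death due to any cause will be censored at the date of the last valid response assessment". The section does not define a valid assessment and does not mention subsequent therapy or transplant. The main analysis set is fixed by "Only subjects with documented CR/CRi/CRp/PR/MLFS response as determined by the IRAC will be included in the analysis", and "Investigator assessed results will be summarized as a supportive analysis".
- **Duration of CR/CRh, SAP 10.3.2.12.** "Subjects without morphologic relapse, PD, or death due to any cause will be censored at the date of the last response assessment".
- **Protocol 9.6.2.2.** The same rule for duration of response: "Subjects without morphologic relapse, PD or death due to any cause will be censored at the date of the last response assessment".
- **Sampling, Protocol 6.3.** Follow-up marrow and response assessment run "until PD, the initiation of the first subsequent AML therapy after discontinuation of study treatment, death, lost to follow-up", among other stopping points. Survival contact continues every 4 weeks. The investigator also reports a relapse or progression date for each later AML therapy.
- **What counts as AML therapy, SAP 8.4.3.** The list includes "consolidation or maintenance therapies, HSCT, low-intensity AML therapies such as azacitidine".
- **EFS, SAP 10.3.1.2.** If new anti-cancer therapy begins before progression or death, "the subject will be censored at the date of last assessment before starting the new anti-cancer therapy". Table 4 applies this equally to subjects who relapse, progress or die after the new therapy.

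**The concern.** Kaplan-Meier estimation needs censoring that carries no information about the outcome still to come. Here, the time after new therapy stays in the risk set only for subjects in whom an event is later recorded. A bridged responder who remains well has that time removed, because the last response assessment came before the therapy. Two subjects with identical histories up to transplant are thus handled differently because of what happens afterwards.

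The rule is neither of the two coherent options. One follows all subjects through new therapy. The other stops all of them at it, as EFS does.

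Bridging is expected in this trial: allogeneic HSCT is a listed reason for ending treatment (Protocol 11.1), and the rate of bridge-to-HSCT is a secondary endpoint (SAP 10.3.2.9). The amendment summary also says that control subjects may receive commercial enasidenib, so subsequent therapy may differ between arms. At stake is how far the reported quartiles of two secondary endpoints can be read as durability of response.

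**Working it through.** The documents give no expected duration of response and no rate of transplant or other therapy among responders, so there is no plan figure to reproduce. The check has four steps.

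**1. Does another clause fill the gap?** SAP 10.3 says secondary time-to-event variables are analysed similarly to OS. SAP 10.2 censors OS at transplant or new therapy only in sensitivity analyses, so no rule for the duration endpoints follows from it.

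**2. Mechanism, by hand (invented data).** Take ten transplanted responders, each with the last marrow at month 2 after response. Four die at months 6, 9, 12 and 15, and six are alive at month 18.
- Survivors followed to month 18: S(15) = 9/10 × 8/9 × 7/8 × 6/7 = 0.60.
- Rule as written, survivors cut back to month 2: S(15) = 3/4 × 2/3 × 1/2 × 0/1 = 0.00.
- EFS rule: all ten are censored at month 2 and none contributes an event.

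The example is extreme because it contains only bridged subjects. Among all responders the effect is diluted.

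**3. Size among all responders (simulation, all inputs assumed).** Without transplant, median duration is 6 months. Transplant falls 1 to 4 months after response in subjects still event-free, with the last marrow 0 to 28 days before it. Follow-up is 7 to 36 months. Post-transplant median survival is 10 or 24 months, and the median time to relapse is 1.5 times that. Cells show median in months / 12-month Kaplan-Meier.

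| Transplanted | Post-transplant median survival | Full follow-up | As written, deaths only | As written, deaths and relapses | EFS rule |
|---|---|---|---|---|---|
| 7.5% | 10 | 6.0 / 0.250 | 6.0 / 0.249 | 5.9 / 0.242 | 5.9 / 0.249 |
| 7.5% | 24 | 6.2 / 0.274 | 6.0 / 0.253 | 6.0 / 0.252 | 5.9 / 0.249 |
| 22.5% | 10 | 6.0 / 0.250 | 6.0 / 0.246 | 5.7 / 0.226 | 5.8 / 0.246 |
| 22.6% | 24 | 6.8 / 0.316 | 6.1 / 0.258 | 6.1 / 0.254 | 5.8 / 0.244 |
| 37.7% | 10 | 6.0 / 0.249 | 6.0 / 0.243 | 5.6 / 0.209 | 5.7 / 0.241 |
| 37.6% | 24 | 7.6 / 0.363 | 6.2 / 0.268 | 6.2 / 0.260 | 5.7 / 0.242 |

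With deaths only, the largest median gaps from full follow-up are 6.2 − 6.0 = 0.2, 6.8 − 6.1 = 0.7 and 7.6 − 6.2 = 1.4 months at the three transplant rates.

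Other assumed inputs give the following (rule as written against full follow-up, deaths only):
- 30% bridged, relapse median 8 months without new therapy. If bridged subjects do well (relapse median 48, death median 36 months), the median is 7.8 v 8.9, a gap of −1.1. If they do badly (5 and 7), it is 7.5 v 6.9, a gap of +0.6.
- 30% bridged, intermediate outcome (12 and 12 months): 6.24 v 6.27.
- 10% bridged: 6.3 v 6.5 with a good outcome and 6.2 v 6.1 with a bad one.

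**4. Direction.** If post-therapy relapses are counted, the rule as written keeps the same events as full follow-up but shrinks the risk sets, so its curve cannot lie above. If only deaths are counted, unseen relapses push the curve up while lost survivor time pushes it down, and either can win.

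**The case against.** The strongest points against are these.

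- **Deaths are not the only post-therapy event that could count.** A reader might infer that a bridged responder counts only by dying and that the relapse dates collected later are discarded. The documents do not support this. Protocol 6.3 collects those dates, the definition of duration of response does not exclude them, and there is a supportive investigator-assessed analysis. The SAP is silent on their use. This stands, but counting them does not cure the problem, as the table shows.
- **The numbers are assumptions.** The SAP reports quartiles, not 12- or 18-month estimates, and on the median the gap is near zero in several settings and changes sign in others. This stands.
- **Full follow-up is one choice of target.** The EFS rule also ignores what happens after new therapy. That is true, but it ignores it for everyone alike. The objection is to selecting on the later outcome, not to the choice of target.
- **Following survivors to last contact may do worse.** A telephone or record contact under Protocol 6.3 shows survival, not remission. In simulation with 30% bridged and half of post-therapy relapses reported, that approach was further from full follow-up than the existing rule in two of three cases. At 18 months the intermediate case gave 0.163 against 0.134 (existing rule 0.119), and the bad case 0.115 against 0.086 (existing rule 0.103). The relapse dates were also added only by a later amendment. This stands, and it is why that approach is unsuitable as the main analysis.
- **Appendix G calls post-remission transplant consolidation.** It does so to count prior lines of therapy. Protocol 6.1 and SAP 8.4.3 both list HSCT as AML therapy. Sites could still read it differently, which is a further reason to write the rule down.

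**Conclusion.** The gap is real. As written, the two duration endpoints censor according to later outcome once a responder starts new therapy, and nothing elsewhere in the SAP repairs this. On assumed inputs the median shifts by about 0 to 0.25 months with 10% of responders bridged and by about 0 to 1 month with 30%. At about 38% transplanted with good outcomes the gap reached 1.4 months. The direction is not settled, because it depends on how bridged subjects fare and on whether the sponsor counts post-therapy relapse.

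A reader might also infer that the trial's comparative conclusions are biased. The documents do not support that. Both duration endpoints are Kaplan-Meier summaries by arm with no test specified, they are restricted to responders (so not a randomised comparison under any censoring rule), and they lie outside the OS, ORR, EFS sequence in SAP 10.1. The type I error rate and the 250-death design are untouched. The point deserves correction as a matter of sound estimation, not as a threat to the primary result.

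**What to change.** In SAP 10.3.2.1 and 10.3.2.12, apply the EFS rule. Any responder who starts subsequent anti-cancer therapy, including HSCT, before relapse or PD is censored at the last response assessment on or before that therapy, whether or not the subject later dies. Define a valid assessment, and state that HSCT counts as subsequent therapy for this purpose.

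As a sensitivity analysis, ignore new therapy. Count death and investigator-reported post-therapy relapse or PD as events, and censor event-free subjects at their last disease-status or survival contact. Note beside it that post-therapy relapse is investigator-reported rather than IRAC-assessed, and may be incomplete for subjects treated before the amendment that added its collection.

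The cost is SAP wording and modest reprogramming of two endpoints; no new data are needed. The main estimate would not describe durability after transplant. It would also assume that bridged responders are otherwise like the rest, and it gives up the short interval between the last marrow and the new therapy. In the table, where bridging was unrelated to prognosis by construction, the EFS-rule median was 5.7 to 5.9 months against the assumed 6.
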